8.10 HIV Virologic Rebound Criteria for Subjects on ARVs

Subjects on ARVs who have at least 2 consecutive post-Day-0 visit plasma HIV-1 RNA levels \geq 1000 copies/mL (at least 2 weeks apart) will be considered to have HIV virologic rebound.

Following an initial HIV-1 RNA result of \geq 1000 copies/mL, subjects on ARVs will be asked to return to the clinic after 2 weeks for a scheduled or unscheduled blood draw for confirmation of HIV virologic rebound. If HIV virologic rebound is confirmed, the blood samples from this visit will be used for HIV-1 genotype/phenotype testing. If no resistance to the subject's current ARV regimen is detected, the subject may continue on current ARV regimen.

HCV study drug should be continued unless safety events warrant the discontinuation of these study drugs, as outlined in section 9.2 of the protocol.

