7.6 Study Visits during treatment

All participants will be seen on days 0, weeks 4, and week 12 EOT, (or week 24 if treated for 24 wks).

- Weeks 4 (+/- 7 days)
- Week 12 [and 16, 20, 24 if applicable] (+/- 10 days)

Plasma HCV RNA will be obtained on each visit. Subjects who fail to achieve >2 log₁₀ HCV RNA drop at this time (unless >2 log drop would be below LLOQ) will be discontinued from therapy unless a review by the PI/Operations Committee determines otherwise.

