7.7 Week 12 or 24 Visit / End of Treatment Visit

Week 12 or 24 will mark the last dose of SOF/LDV to be administered. In addition, if a subject's participation terminates prior to end of treatment, the assessments may be performed at any end-of-treatment visit.

7.7.1 Liver Staging (End of Treatment):

All subjects will have end of treatment liver staging by the same method used to stage at screening.

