11 SCHEDULE OF EVENTS

11.1 Schedule of Events Prospective Arm

	Screening	Day 0	Week 4	Week 12*	Week 24*	Day of Transplant	3M post treatment	6 M post treatment
			Month 1	Month 3	Month 6 if treated for 24 weeks	If transplant occurs post treatment with study drug	3 Months post treatment	6 Months or greater post treatment
History and Physical	X	X	X	X	X			X
Vital signs and Weight		X	X	X	X		X	X
Height	X							
Urinalysis		X						
Pregnancy Test: Urine		X ¹						
HBsAg	X							
Anti-HBc	X							
Virology Panel: (Historical only)								
Anti-HIV Ab	X							
Anti-HCV Ab	X							
HCV Genotype	X							
Plasma HCV RNA Levels		X	X	X	X		X	X
CD4+ T-cell count		X ²		X ²	X ²		X ²	X ²
HIV-1 RNA (bDNA or PCR)		X ²		X ²	X ²		X ²	X ²
Standard of care liver staging	X			X ³	X			
SERUM CHEMISTRY								
Alanine aminotransferase (ALT)		X	X	X	X		X	X
Albumin		X		X	X			X
Alkaline phosphatase		X	X	X	X		X	X
Aspartate aminotransferase (AST)		X	X	X	X		X	X
Bicarbonate (If on ARV regimen containing tenofovir)		X	X	X	X		X	X
Bilirubin, total, direct		X	X	X	X		X	X
Glucose (repeat during treatment, but only if abnormal at baseline)		X	X	X	X			
Phosphate (If on ARV regimen containing tenofovir)		X	X	X	X		X	X
Potassium (If on ARV regimen containing tenofovir)		X	X	X	X		X	X
Sodium		X	X	X	X		X	X
Serum Creatinine		X	X	X	X		X	X
HEMATOLOGY								
Hemoglobin		X		X	X			
Platelet Count		X		X	X			
White Blood Cell (WBC) Count		X		X	X			
Differential		X		X	X			
Neutrophils		X		X	X			
Lymphocytes		X		X	X			
INR		X		X	X			
RESEARCH								

Limited HCV Viral Kinetics		X	X	X	X			
Liver explant tissue (if achieved SVR)						X ⁴		
HLA	X ²							
Blood draw for immunologic studies		X	X	X	X		X	X
Paxgene DNA (6.5 ml)		X						
Paxgene RNA (2.5 ml)		X	X	X	X		X	
IL28B rs12979860 (run off Paxgene DNA sample)		X						
Blood for storage (8 cc SST serum, 6 cc EDTA)		X	X	X	X		X	X

*Subjects who are terminated early or who have early treatment discontinuation should have an end of treatment visit as soon as possible after therapy is stopped.

¹ Urine pregnancy test for females with childbearing potential must be negative on Day 0 prior to dosing with study agent

² documented historic results are acceptable. If not available, not required unless considered standard of care, or may be run on stored samples. For HIV-1 RNA and CD4+ T-cell counts, test results from primary care provider should be obtained per standard of care (every 3 months)

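### Section 8.10 defines HIV rebound from post-Day-0 HIV-1 RNA values, but the prospective schedule does not guarantee one, so rebound may be detected late or missed

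*Combined protocol and SAP*

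**What the plan says.** Section 8.10 applies to subjects on antiretrovirals. Rebound requires "at least 2 consecutive post-Day-0 visit plasma HIV-1 RNA levels" at or above 1000 copies/mL, at least 2 weeks apart. After a first high result the subject "will be asked to return to the clinic after 2 weeks for a scheduled or unscheduled blood draw for confirmation of HIV virologic rebound". Confirmed rebound leads to HIV resistance testing on that sample. HCV study drug goes on unless safety events call for stopping it.

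The prospective schedule in 11.1 marks HIV-1 RNA at Day 0, Week 12, Week 24, and 3 and 6 months post treatment. Week 4 is blank. Every marked cell carries footnote 2, which reads "documented historic results are acceptable. If not available, not required unless considered standard of care, or may be run on stored samples". A further sentence of the footnote, specific to this test and the CD4 count, adds that "test results from primary care provider should be obtained per standard of care (every 3 months" (its closing bracket follows).

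On visit timing, 7.6 says "All participants will be seen on days 0, weeks 4, and week 12 EOT" (or Week 24 for the longer course), with a window of 10 days either side from Week 12 on. Section 7.7 says "Week 12 or 24 will mark the last dose of SOF/LDV to be administered".

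**The concern.** The rule in 8.10 can start only from an HIV-1 RNA value obtained after Day 0. A result from before treatment cannot count towards it. Footnote 2 sets no age limit on a historic result, so a pre-treatment value could fill the Week 12 cell and leave the rule with nothing to act on. If no result exists, the footnote waives the test unless it is standard of care.

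The allowance looks like a screening provision carried forward. Section 7.1 describes the use of historic HIV viral load and CD4 results under screening, and the schedule then attaches the same note to the on-treatment and post-treatment visits. The plasma HCV RNA row in the same table carries no such note.

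At stake is how the HIV safety data can be read. Under 5.2, subjects on antiretrovirals enter with HIV below detection. Safety is part of both primary objectives, and the introduction cites the absence of HIV breakthrough in an earlier SOF/LDV study of coinfected subjects as support. If post-Day-0 results are stale or absent in some of the 10 to 20 prospective patients, an absence of recorded rebound could not be read as an absence of rebound.

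**Working it through.** The plan states no statistical figure on this point, so there is none to reproduce. The check is a count of schedule cells and some day arithmetic.

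**Inputs**
- Confirmation interval: 14 days (8.10).
- HIV-1 RNA cells after Day 0: Week 12, Week 24, and 3 and 6 months post treatment, all with footnote 2 (11.1).
- Visit window from Week 12 on: 10 days either side (7.6).
- Last dose: Week 12 or Week 24 (7.7), that is 12 × 7 = day 84 or 24 × 7 = day 168.

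**Scheduled on-treatment values after Day 0**
- 12-week course: one (Week 12, which is also end of treatment).
- 24-week course: two (Weeks 12 and 24). Section 7.6 also names Weeks 16 and 20, but 11.1 has no column for them.
- From Day 0 to the first scheduled value: 84 − 10 = 74 days at the earliest, 84 + 10 = 94 at the latest.

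**Earliest confirmation = day of first high value + 14**

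| Course and visit | First value | Confirmation | Planned last dose | On drug? |
|---|---|---|---|---|
| 12 weeks, earliest Week 12 visit | day 74 | 74 + 14 = day 88 | about day 84 | No |
| 12 weeks, nominal Week 12 visit | day 84 | 84 + 14 = day 98 | about day 84 | No |
| 24 weeks, nominal Week 12 visit | day 84 | 84 + 14 = day 98 | about day 168 | Yes |
| 24 weeks, latest Week 12 visit | day 94 | 94 + 14 = day 108 | about day 168 | Yes |
| 24 weeks, earliest Week 24 visit | day 158 | 158 + 14 = day 172 | about day 168 | No |

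**What primary-care results could add.** This is an illustration on assumptions that the documents do not give: tests exactly every 91 days, timing uniform relative to Day 0, and every test done and collected.
- First post-Day-0 test by day 84: 84/91 = 92% of patients.
- First post-Day-0 test by day 70 (84 − 14, early enough to confirm on drug in a 12-week course): 70/91 = 77%.
- Taking 3 months as 90 to 92 days gives 91% to 93% and 76% to 78%.

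These shares fall if tests are missed, not collected, or replaced by an older historic value.

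**The case against.** A reader might infer more than the documents support, and four such readings should be set aside.

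- **That a missing result is simply allowed at every later visit.** The waiver holds only where the test is not standard of care, and the same footnote describes HIV-1 RNA every 3 months as standard of care. That interval is close to the 12-week visit spacing. The footnote pulls two ways; it does not plainly excuse the test.
- **That two scheduled values are needed.** One high value triggers a return draw, which may be unscheduled. Only the first value depends on the schedule or on primary care.
- **That rebound can never be confirmed on drug in a 12-week course.** This is true only of a rebound first seen at the scheduled Week 12 visit. Nothing in 8.10 confines the first value to a study visit, and a primary-care result by about day 70 would leave time.
- **That treatment decisions or the efficacy result are at risk.** Under 8.10, rebound alone does not stop HCV drug, and resistance testing can run on the confirmatory sample whenever it is drawn. HIV rebound is not among the endpoints in 3.3 or 4.1.1 to 4.1.4.

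All four objections stand. They narrow the point but do not remove it. The primary-care sentence is worded as an expectation. It sets no visit window, does not require the result to post-date Day 0, and does not say who is evaluable. Testing stored blood is optional.

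**Conclusion.** The point holds in a limited form. The protocol does not guarantee a dated, on-treatment, post-Day-0 HIV-1 RNA value to trigger 8.10, so rebound may be detected late or missed. Between Day 0 and the first scheduled value there are 74 to 94 days. In a 12-week course a rebound first seen at that visit is confirmed on day 88 at the earliest, about 4 days after planned dosing ends (88 − 84). In a 24-week course a high Week 12 value can be confirmed on drug, but one first seen at Week 24 cannot.

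The timing rests on planned treatment lengths, the stated windows and the 2-week interval. How many patients would lack a usable value cannot be derived, because the documents do not say how regularly primary-care tests are done or collected. The consequence is confined to HIV safety ascertainment in the prospective arm. The change is inexpensive and worth making; it does not correct any planned analysis.

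**What to change.** Reconcile 8.10 with 11.1 and footnote 2:

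1. Limit the undated historic or not-required allowance to the baseline HIV-1 RNA.
2. For the HIV-1 RNA cells already scheduled after Day 0, record a result dated after Day 0 and within the visit window. Where no clinic result exists, use plasma stored at that visit. The schedule already collects blood for storage at each of these visits, and footnote 2 already permits testing it.
3. State in 8.10 which results count towards the rule, including whether primary-care values do, and whether on-treatment rebound is regarded as assessable in 12-week courses.
4. Give any count of rebound over patients with evaluable post-Day-0 values, and report how many have none.

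This adds no visit and leaves dosing and treatment rules as they are. The cost is a few extra assays in 10 to 20 patients. One limit remains: a stored-sample result may come too late to support the 2-week confirmation draw. Such results would make the safety report interpretable but would not ensure detection during treatment.

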8.11 Concomitant Medications

Concomitant medications taken within 30 days of screening through 30 days following discontinuation of study treatment need to be recorded in the source documents.

The medications listed in Table 2 are prohibited from 28 days prior to the Day 0 (start of treatment) visit through the end of treatment:

- Concomitant use of certain medications or herbal/natural supplements (inhibitors or inducers of drug transporters i.e., P-gp) with study drug(s) may result in pharmacokinetic interactions resulting in increases or decreases in exposure of study drug(s). Examples of representative medications which are prohibited from 28 days prior to Day 0 (start of treatment) through the end of treatment are listed below:
- Medications for disease conditions **excluded** from the protocol are not listed under this Concomitant Medication section and are disallowed in the study.

Note: Since this table is likely to change over time, please review the most current package inserts before prescribing new drugs or modifying doses of concomitant medications.

Table 2: Potentially Significant Drug Interactions: Alteration in Dose or Regimen May be Recommended Based on Drug Interaction Studies or Predicted Interactions^a

Concomitant Drug Class: Drug Name	Clinical Comment
Acid Reducing Agents	Ledipasvir solubility decreases as pH increases. Drugs that increase gastric pH are expected to decrease concentration of ledipasvir.
Antacids (e.g., aluminum and magnesium hydroxide)	It is recommended to separate antacid and HARVONI administration by 4 hours.

H2-receptor antagonists ^b (e.g., famotidine)	H2-receptor antagonists may be administered simultaneously with or 12 hours apart from HARVONI at a dose that does not exceed doses comparable to famotidine 40 mg twice daily.
Proton-pump inhibitors ^b (e.g., omeprazole)	Proton-pump inhibitor doses comparable to omeprazole 20 mg or lower can be administered simultaneously with HARVONI under fasted conditions.
Antiarrhythmics : digoxin amiodarone	Coadministration of HARVONI with digoxin may increase the concentration of digoxin. Therapeutic concentration monitoring of digoxin is recommended when coadministered with HARVONI. Coadministration of HARVONI with amiodarone may result in serious symptomatic bradycardia. The mechanism of this effect is unknown. Coadministration of amiodarone with HARVONI is not recommended; if coadministration is required, cardiac monitoring is recommended.
Anticonvulsants: carbamazepine phenytoin phenobarbital oxcarbazepine	Coadministration of HARVONI with carbamazepine, phenytoin, phenobarbital, or oxcarbazepine is expected to decrease the concentration of ledipasvir and sofosbuvir, leading to reduced therapeutic effect of HARVONI. Coadministration is not recommended.
Antimycobacterials: rifabutin rifampin ^b rifapentine	Coadministration of HARVONI with rifabutin or rifapentine is expected to decrease the concentration of ledipasvir and sofosbuvir, leading to reduced therapeutic effect of HARVONI. Coadministration is not recommended. Coadministration of HARVONI with rifampin, a P-gp inducer, is not recommended
HIV Antiretrovirals	
efavirenz, emtricitabine, tenofovir disoproxil fumarate (DF)	Monitor for tenofovir-associated adverse reactions in patients receiving HARVONI concomitantly with the combination of efavirenz, emtricitabine and tenofovir DF. Refer to VIREAD, TRUVADA, or ATRIPLA prescribing information for recommendations on renal monitoring.
Regimens containing tenofovir DF and a HIV protease inhibitor/ritonavir 
atazanavir/ritonavir + emtricitabine/tenofovir DF^bdarunavir/ritonavir + emtricitabine/tenofovir DF^blopinavir/ritonavir + emtricitabine/tenofovir DF	The safety of increased tenofovir concentrations in the setting of HARVONI and a HIV protease inhibitor/ritonavir has not been established. Consider alternative HCV or antiretroviral therapy to avoid increases in tenofovir exposures. If coadministration is necessary, monitor for tenofovir-associated adverse reactions. Refer to VIREAD or TRUVADA prescribing information for recommendations on renal monitoring.
elvitegravir, cobicistat, emtricitabine, tenofovir DF	The safety of increased tenofovir concentrations in the setting of HARVONI and the combination of elvitegravir, cobicistat, emtricitabine and tenofovir DF has not been established. Coadministration is not recommended.
tipranavir/ritonavir	Coadministration of HARVONI with tipranavir/ritonavir is expected to decrease the concentration of ledipasvir and sofosbuvir, leading to reduced therapeutic effect of HARVONI. Coadministration is not recommended.
HCV Products: Simeprevir ^b	Concentrations of ledipasvir and simeprevir are increased when simeprevir is coadministered with ledipasvir. Coadministration of HARVONI with simeprevir is not recommended.
Herbal Supplements: St. John's wort (Hypericum perforatum)	Coadministration of HARVONI with St. John's wort, a P-gp inducer is not recommended

HMG-CoA Reductase Inhibitors rosuvastatin	Coadministration of HARVONI with rosuvastatin may significantly increase the concentration of rosuvastatin which is associated with increased risk of myopathy, including rhabdomyolysis. Coadministration of HARVONI with rosuvastatin is not recommended.
---	---

a. This table is not all inclusive.
 b. These interactions have been studied in healthy adults.

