3.3 STUDY ENDPOINTS

3.3.1 Primary Endpoints

- Safety and tolerability of SOF/LDV for 12 to 24 weeks
- Proportion of subjects achieving SVR₁₂ (HCV RNA < LLOQ 12 weeks after completion of treatment)

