4.1.1 Primary Endpoint

The primary efficacy endpoint is SVR₁₂ (HCV RNA < LLOQ 12 weeks after cessation of therapy).

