4.2.1 Efficacy Population

The primary analysis population for efficacy analysis will be defined as all participants who received at least one dose of study drug.

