4.3 Data Handling Conventions

Missing data can have an impact upon the interpretation of the trial data. Other than the endpoints discussed below, values for missing data will not be imputed.

For the analysis of post-baseline categorical efficacy endpoints, if a data point is missing and is preceded and followed in time by values that are deemed successes, then the missing data point will be termed a success; otherwise the data point will be termed a failure.

Any subject with missing data due to premature discontinuation of the study medication will be considered a failure at the time points on, or following, the date of discontinuation. If no HCV RNA values are obtained after the last dose of study medication, the subject will be considered a treatment failure for the SVR endpoints.

Where appropriate, safety data for subjects that did not complete the study will be included in summary statistics. For example,

- If a subject received study medication, the subject will be included in a summary of adverse events according to the treatment received; otherwise, if the subject is not dosed then they will be excluded from the summary.
- If safety laboratory results for a subject are missing for any reason at a time point, the subject will be excluded from the calculation of summary statistics for that time point. If the subject is missing a pre-dose value, then the subject will be excluded from the calculation of summary statistics for the pre-dose value and the change from pre-dose values.

Values for missing vital signs data will not be imputed; however, a missing Day 0 result will be replaced with a screening result, if available.

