4.4 Efficacy Analyses

4.4.1 Primary Analysis

The primary efficacy endpoint is SVR₁₂ (HCV RNA <LLOQ 12 weeks after cessation of therapy.)

There is no active comparator group for this study (as in most clinical trials with all oral therapies in these populations).

In the primary efficacy analysis, an exact Clopper-Pearson 95% confidence interval will be computed for the SVR₁₂ rate.

The primary analysis will be performed after all enrolled subjects have been followed through 12 weeks post-treatment or discontinued from study.

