8.6 Treatment of Participants

All participants will receive 12 or up to 24 weeks of SOF/LDV. SOF/LDV will be administered as a single pill at dose of 400 mg and 90 mg respectively orally once a day. It can be taken with or without food.

If a participant who starts treatment with study drug prior to transplant receives 4 weeks of treatment or less prior to transplant and has detectable HCV at time of transplant, they are eligible to receive full treatment post-transplant.

If a participant who starts treatment with study drug prior to transplant has received more than 4 weeks of treatment prior to transplant, they are NOT eligible to receive full treatment post-transplant, regardless of HCV RNA level at the time of liver transplantation. Therefore, study treatment is discontinued at the time of transplant.

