8.9 Criteria Requiring Discontinuation of SOF/LDV

Subjects will be considered treatment failures and will discontinue SOF/LDV if they meet any of the following criteria while taking study drugs:

- Plasma HCV RNA greater than LLOQ after 2 prior consecutive HCV RNA values less than the LLOQ
- Greater than a $1 \log_{10}$ increase in plasma HCV RNA from nadir
- Less than a $2 \log_{10}$ decline in HCV RNA after 4 weeks of treatment

If any of these should occur in a subject who is currently on study drugs, the subject should return within one week for a confirmatory test. If the confirmatory test also meets the same criteria, the subject will be considered a treatment failure and should be discontinued from therapy. Participants will be referred for other treatment options. The anticipated clinical impact of discontinuation should be discussed in advance if possible, particularly if discontinuation is thought to pose a risk to the overall clinical wellbeing of the subject. Those who are discontinued will continue to follow the general study schedule of assessments unless unwilling to do so, in which case they may be seen at least every 12 weeks for safety and research labs until the end of the study. Subjects will be followed closely for resolution of active laboratory abnormalities or adverse events that are considered related to the study agents prior to starting the revised schedule.

Subjects who meet any of the following laboratory criteria must stop all study medication(s):

- Any Grade 3 or greater rash associated with constitutional symptoms
- Any Grade 4 event assessed as possibly, probably, or definitely related to treatment with SOF or LDV

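### Sections 4.3 and 4.4.1 give no SVR12 rule for an HCV RNA below LLOQ measured after a prospective participant has started non-study anti-HCV therapy

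*Combined protocol and SAP*

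**What the plan says.** **Endpoint and population.** Section 3.3.1 defines SVR12 as "HCV RNA < LLOQ 12 weeks after completion of treatment" and section 4.4.1 as "HCV RNA <LLOQ 12 weeks after cessation of therapy". Neither sets a condition on other anti-HCV drugs. The efficacy population in 4.2.1 is "all participants who received at least one dose of study drug", so participants who stop early stay in the denominator.

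**Failure by data handling.** Section 4.3 states: "Any subject with missing data due to premature discontinuation of the study medication will be considered a failure", from the date of discontinuation onward. It also makes a participant with no HCV RNA after the last dose a failure for SVR. Both rules need absent data.

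**Failure by virologic criteria.** Section 8.9 calls confirmed on-treatment virologic failures treatment failures, keeps them on the assessment schedule, and adds: "Participants will be referred for other treatment options". Section 8.9.1 adds detectable HCV RNA after treatment in those below LLOQ at its end.

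**Other reasons for stopping.** Section 8.7 ends treatment for toxicity or an interruption of more than 5 days. Section 8.6 ends it at transplant after more than 4 weeks of treatment; of these participants it says "they are NOT eligible to receive full treatment post-transplant, regardless of HCV RNA level at the time of liver transplantation". Section 7.10 offers continued follow-up to those who stop for medical or personal reasons. None of these sections assigns an efficacy outcome.

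**Drug records.** Section 8.11: "Concomitant medications taken within 30 days of screening through 30 days following discontinuation of study treatment need to be recorded in the source documents". Section 7.5 has participants asked at each visit about medication since the previous one. The prospective schedule (11.1) has no concomitant-medication row. Post-treatment visits are at Weeks 12 and 24, +/- 14 days (7.9).

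**The concern.** The prospective arm is meant to estimate SVR12 on SOF/LDV, with no comparator. If a participant stops SOF/LDV early, starts another regimen and is below LLOQ at post-treatment Week 12, the response may belong to the second regimen, or may be suppression while still taking it. As written, the value meets the SVR12 definition. Compared with counting such participants as non-responders, the written rule can only raise the estimate, and SVR24 is exposed in the same way. If the later drug is not recorded, the analyst may not be able to identify the case.

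**Working it through.** **1. The plan's own figure.** Table 1 in 4.1 gives exact 95% intervals at n=50. Clopper-Pearson: lower limit = Beta quantile 0.025 with parameters (x, n-x+1); upper limit = Beta quantile 0.975 with parameters (x+1, n-x).

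| SVRs of 50 | Table 1 | Recomputed |
|---|---|---|
| 50 | 0.929-1 | 0.9289-1 |
| 48 | 0.863-0.995 | 0.8629-0.9951 |
| 46 | 0.808-0.978 | 0.8077-0.9778 |
| 44 | 0.757-0.955 | 0.7569-0.9547 |
| 42 | 0.709-0.928 | 0.7089-0.9283 |
| 40 | 0.663-0.900 | 0.6628-0.8997 |

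All six reproduce. The interval method is sound; the question is what goes into the numerator.

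**2. Tracing a switcher through the rules.** Take a participant with a measured Week 12 value below LLOQ who has started a non-study anti-HCV drug.

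| Reason for stopping | Failure label | SVR12 as written |
|---|---|---|
| Confirmed on-treatment virologic failure (8.9) | Treatment failure | Not settled: 4.3 and 4.4.1 do not link the label to SVR12 |
| Toxicity, or interruption over 5 days (8.7) | None | Success |
| Transplant after more than 4 weeks (8.6) | None | Success |
| Medical or personal choice (7.10) | None | Success |

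The missing-data rules in 4.3 do not apply, because the value exists. Section 4.4.2 defers detail to a statistical analysis plan, but the document supplied holds no further rule on this.

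**3. The recording window.** The duty in 8.11 ends on day 30 after stopping.
- SVR12 is due at 12 x 7 = 84 days, window 70 to 98. Days outside the duty: 84 - 30 = 54 (54/84 = 64%), or 40 to 68 across the window.
- SVR24 is due at 24 x 7 = 168 days. Days outside the duty: 168 - 30 = 138 (138/168 = 82%).
- As an illustration only, a 12-week course starting on day 31 would run to day 31 + 83 = 114 and cover the whole SVR12 window.

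These counts describe the duty in 8.11 only. The enquiry in 7.5 spans the same days.

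**4. Size.** One switcher counted as a success adds 1/n: 1/10 = 10 points and 1/20 = 5 points (the prospective arm is 10 to 20, section 3.0), and 1/50 = 2 points for the pooled sample in 4.1. The documents do not give the number of switchers, k, so 0 to 3 is an assumption. Starting from all participants counted as successes and reclassifying k of them:

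| n | k=0 | k=1 | k=2 | k=3 |
|---|---|---|---|---|
| 10 | 100% (0.692-1) | 90% (0.555-0.997) | 80% (0.444-0.975) | 70% (0.348-0.933) |
| 20 | 100% (0.832-1) | 95% (0.751-0.999) | 90% (0.683-0.988) | 85% (0.621-0.968) |
| 50 | 100% (0.929-1) | 98% (0.894-0.999) | 96% (0.863-0.995) | 94% (0.835-0.987) |

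From a lower start, reclassifying two of 18/20 gives 16/20: 90% (0.683-0.988) becomes 80% (0.563-0.943).

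**The case against.** The strongest case against has four parts.

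- **Missing data are not the only route to failure.** A reader might infer from 4.3 that they are. Sections 8.9 and 8.9.1 label virologic failures with no missing-data condition, and 4.3 uses the same term for the SVR endpoints. Reading an 8.9 failure as an SVR success is therefore strained, and the defect for that group is a missing cross-reference. This stands.
- **The one stated referral to other therapy concerns that labelled group.** No section says that toxicity or transplant stops go on to other HCV drugs. Section 15.2 lists alternatives to joining the study, not care after stopping. Section 1.1 does say that HCV treatment is often started after transplant, which makes the route plausible, but its frequency is unknown. This stands as a limit on size.
- **The drug data may exist.** A reader might infer that the analyst could never identify switchers. Section 7.5 has no 30-day limit, and section 19 counts medical and pharmacy records as source documents, so that inference fails. What remains is that 7.5 requires asking and not recording, that 8.11 stops at day 30, and that 11.1 has no row for it.
- **The arm is small and descriptive, with no hypothesis test.** In the pooled n=50, one participant moves the estimate by only 2 points. That lowers the severity but does not classify the value.

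**Conclusion.** The gap is real but narrow. For prospective participants who stop SOF/LDV for non-virologic reasons and then start another anti-HCV drug, a measured value below LLOQ at Week 12 is an SVR12 success under the written rules. For virologic failures under 8.9 the label exists but is not connected to the endpoint. Sections 7.5 and 8.11 do not agree on how long medication information must be kept and need to be reconciled.

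The size is 10, 5 or 2 percentage points per participant at n=10, 20 or 50. It rests on at least one participant switching before the sample and being below LLOQ; the documents give no count, and it may be zero. They therefore do not support saying that the SVR12 estimate will be inflated, only that nothing in 4.3 or 4.4.1 prevents it. This should be settled before the primary analysis, but it does not undermine the design.

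**What to change.** 1. **Add a classification rule to 4.3.**
   - A participant who starts any non-study anti-HCV drug after the first dose and before the SVR4, SVR12 or SVR24 sample is a non-responder for that and later SVR endpoints, whatever the HCV RNA value.
   - A confirmed on-treatment virologic failure under 8.9 is a non-responder for all SVR endpoints.
   - Post-treatment relapse, defined as HCV RNA at or above LLOQ, is a failure only for SVR time points at or after the relapse. The time limit is needed because follow-up runs to 36 weeks for late relapse (3.2), and someone who met SVR12 and relapsed later should keep SVR12. The LLOQ threshold is needed because 8.9.1 says detectable, which could reclassify values that are detectable but below LLOQ.
2. **Fix the clock.** Count the 12 and 24 weeks from the last dose of study drug, and state how SVR is counted for participants who repeat study drug after transplant under 8.6.
3. **Record the drugs.** Keep the 30-day window in 8.11 for general medication, but record the name, start date and stop date of any anti-HCV drug through the last follow-up visit, and align 7.5 and 11.1 with this.

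The cost is a short addition to 4.3 and one extra data item at existing visits. The SVR12 figure may be slightly less favourable, partly because a participant already cured by a shortened course who then starts another drug would count as a non-responder. None of this changes how participants are treated.
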